10.1. Source Data	27
10.2 Language	28
10.3. Data Collection	28
10.6. Monitoring.....	28
11. DISCLOSURE OF DATA AND PUBLICATION	29
12. REFERENCES	31

	Title: DIAPLATE-STUDY	Protocol No: Version 3.5	Sponsor: Medical University of Graz	Date: 13th February 2018
--	--------------------------	-----------------------------	--	-----------------------------

Abbreviations

AE	Adverse event
ACTH	Adrenocorticotropic hormone
BMI	Body mass index
CRF	Case report form
CRH	Counter regulatory hormones
EC	Ethical Committee
ECG	Electrocardiography
FPPV	First patient first visit
FPLV	First patient last visit
GIR	Glucose infusion rate
HbA1c	Glycated haemoglobin 1c
HSS	Hypoglycaemic symptoms score
ICAM	Intercellular adhesion molecule
IGF-1	Insulin-like-growth factor 1
IL-6	Interleukin-6
PAI-1	Plasminogen activator inhibitor
PAP	Platelet activity parameters
PTH	Parathyroid hormone
PG	Plasma glucose
SDF	Source data form
T2DM	Type 2 Diabetes Mellitus
TMF	Trial master file
VCAM	Vascular adhesion molecule
vWF	von Willebrand factor

Sponsor	Medical University of Graz [name] 8036 Graz, Austria
Principal Investigators	[name], Associate Professor
Indication	Type 2 diabetes mellitus without history of cardiovascular disease
Study design and phase	Monocentric, single arm, open, mechanistic trial
Study Short Title	Platelet activity during hypoglycaemia
Keyword	Hypoglycaemia, platelet activity, type 2 diabetes mellitus
Aims of the trial	
Primary objective:
 
 - The primary objective is to investigate platelet activation during different levels of hypoglycaemia induced by a stepwise hyperinsulinaemic, hypoglycaemic clamp experiment in patients with T2DM 
Secondary objective:
 
To investigate
 
 - Platelet activation and recovery at one day and one week after the clamp experiment - Changes of proatherothrombotic markers during the hypoglycaemic clamp - Counter regulatory hormone response during the clamp
Outcome measures of the trial	
Primary outcome measures:
 
 - Changes in platelet activation measured by light transmittance aggregometry based on ADP activation from baseline to the end of the hypoglycaemia phase (i.e. 45 mg/dl for 30 minutes) (visit 3) 
Secondary outcomes measures:
 
 - Changes in platelet activation measured by activation marker, such as CD62P, CD63 and PAC1, on CD41^{pos} or CD42b^{pos} platelets from baseline to the end of the hypoglycaemia phase - Changes in platelet activation measured by activation marker, such as LTA, CD62P, CD63 and PAC1, on CD41^{pos} or CD42b^{pos} platelets from the end of the hypoglycaemic clamp to one day after the clamp - Changes in platelet activation measured by activation marker, such as LTA, CD62P, CD63 and PAC1, on CD41^{pos} or CD42b^{pos} platelets from the end of the hypoglycaemic clamp to one week after the clamp - Changes in platelet activation measured by PFA-100 from baseline to the end of the hypoglycaemia phase - Changes in platelet activation measured by PFA-100 from the end of the hypoglycaemic clamp to one day and one week after the clamp - Changes in interleukin-6 (IL-6), von Willebrand factor [vWF], plasminogen activator inhibitor (PAI-1), vascular adhesion molecule (VCAM) and intercellular adhesion molecule (ICAM) from baseline to the end of the hypoglycaemia phase

	
 - Changes in interleukin-6 (IL-6), von Willebrand factor [vWF], plasminogen activator inhibitor (PAI-1), vascular adhesion molecule (VCAM) and intercellular adhesion molecule (ICAM) from the end of the hypoglycaemic clamp to one week after the clamp - Difference of platelet activation parameters during different states of hypoglycaemia - Counter regulatory hormone response during hypoglycaemia
Number of patients	
 - 14
Time schedule	
 - EC Submission: SEP/2017 - Local Authority Submission.: SEP/2017 - First Patient In (FPFV): JAN/2018 - Last Patient In: APR/2018 - Last Patient Out (LPLV): MAY/2018 - Data Base Lock: JUL/2018 - First Results available: JUL/2018 - Clinical Study Report: DEC/2018
Main inclusion criteria	
 - Male or female aged 18-64 years (both inclusive) at the time of signing informed consent. - Subjects diagnosed with type 2 diabetes (defined by WHO-criteria) and on stable treatment for a period of 90 days prior to screening with metformin as monotherapy or diet only. Stable is defined as unchanged dose. - Body mass index (BMI) between 20.0 and 35.0 kg/m² (both inclusive). - HbA1c between 43 and 64 mmol/mol (6.0% – 8.0%) (both inclusive). - No use of platelet inhibiting therapy (e.g. aspirin, clopidogrel, ticagrelor, prasugrel)
Main exclusion criteria	
 - All other forms of diabetes (type 1 diabetes, gestational diabetes) than type 2 diabetes mellitus. - Treatment with any glucose lowering agent(s) other than metformin in a period of 60 days prior to screening. An exception is short-term treatment (\leq 7 days in total) with insulin due to intercurrent illness. - Clinically significant abnormal haematology, platelet count, biochemistry and coagulation. - Uncontrolled hypertension defined as resting blood pressure at screening (after resting for 5 min) outside the range of 90–160 mmHg for systolic or 50–100 mmHg for diastolic. - Chronic liver failure as assessed by the investigator. - ALT or AST levels $>$ 3x ULN - Previously known cardiovascular disease and / or past cardiovascular events, or past episodes of a congestive heart failure syndrome (NYHA II - NYHA IV) - Females of child bearing potential without adequate contraceptive methods (i.e. sterilisation, intrauterine device, vasectomised partner; or medical history of hysterectomy) - eGFR $<$ 45 ml/min/1,73 m²

	
- Treatment with beta-blockers, antiarrhythmic agents or neuroleptic drugs- Active smoker or intake of illicit substances.- Regular NSAR/NSAID intake
--	---

Confidential

	Title: DIAPLATE-STUDY	Protocol No: Version 3.5	Sponsor: Medical University of Graz	Date: 13th February 2018
--	--------------------------	-----------------------------	--	-----------------------------

1. INTRODUCTION AND RATIONALE

Increased platelet activation is significantly involved in the pathophysiology of micro- and macrovascular diabetic complications. Previously performed studies suggested platelet activation in both, hyper- and hypoglycaemic states, leading to a potentially increased risk for thromboembolic complications. Hypoglycaemia, in particular severe hypoglycaemic episodes, has been associated with increased cardiovascular or overall mortality in previous studies [6, 7]. Potential mechanisms include arrhythmias or increased risk for thrombembolism, based on platelet activation and/or hypercoagulability.

However, studies investigating the effect of hypoglycaemia on platelet activity were mainly performed in healthy individuals or subjects with type 1 diabetes ([3],4,5]). In addition these studies did not systematically evaluate the correlation between the degree of hypoglycaemia and platelet activation in subjects with type 2 diabetes and the sustainability of platelet activation after the hypoglycaemic event.

Data on the impact of hypoglycaemia on platelet activation and markers of pro-atherothrombotic biomarkers in subjects with T2DM are scarce. Therefore we aim to explore platelet activation and atherothrombotic biomarkers during a stepwise hypoglycaemic clamp in subjects with T2DM and without established cardiovascular disease. In addition we aim to investigate for how long these potential effects sustain after the hypoglycaemic event.

Secondary objectives are to explore associations of the extent of hypoglycaemia and counter regulatory response and platelet activation.

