2.4 SECONDARY OUTCOMES

- Changes in platelet activation measured by activation marker, such as CD62P, CD63 and PAC1, on CD41^{pos} or CD42b^{pos} platelets from baseline to the end of the hypoglycaemia phase
- Changes in platelet activation measured by activation marker, such as LTA, CD62P, CD63 and PAC1, on CD41^{pos} or CD42b^{pos} platelets from the end of the hypoglycaemic clamp to one day after the clamp
- Changes in platelet activation measured by activation marker, such as LTA, CD62P, CD63 and PAC1, on CD41^{pos} or CD42b^{pos} platelets from the end of the hypoglycaemic clamp to one week after the clamp
- Changes in platelet activation measured by PFA-100 from baseline to the end of the hypoglycaemia phase
- Changes in platelet activation measured by PFA-100 from the end of the hypoglycaemic clamp to one day and one week after the clamp
- Changes in interleukin-6 (IL-6), von Willebrand factor [vWF], plasminogen activator inhibitor (PAI-1), vascular adhesion molecule (VCAM) and intercellular adhesion molecule (ICAM) from baseline to the end of the hypoglycaemia phase
- Changes in interleukin-6 (IL-6), von Willebrand factor [vWF], plasminogen activator inhibitor (PAI-1), vascular adhesion molecule (VCAM) and intercellular adhesion molecule (ICAM) from the end of the hypoglycaemic clamp to one week after the clamp
- Difference of platelet activation parameters during different states of hypoglycaemia
- Counter regulatory hormone response during hypoglycaemia

	Title: DIAPLATE-STUDY	Protocol No: Version 3.5	Sponsor: Medical University of Graz	Date: 13th February 2018
--	--------------------------	-----------------------------	--	-----------------------------

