At approximately 07:00 in the morning, two intravenous cannulas (catheters) will be inserted: one cannula will be inserted in an antecubital vein of a forearm for sampling of serial measurements of plasma glucose (approximately every 5-30 min, depending on the clamp procedure and safety). The hand will be placed in a heated environment to enable drawing of arterialised-venous blood. For controlled variable infusion of glucose 20% and infusion of human soluble insulin (40 IU Actrapid®, 100 IU/ml in 99.6 mL saline), an antecubital vein of the contralateral arm will be cannulated. Both cannulas will be kept open by a slow continuous 0.9% saline infusion. After the baseline blood samples for blood glucose, insulin and platelet activity have been taken (timepoint 0 min), the hyperinsulinemic – euglycemic clamp will be started. A variable i.v. infusion of glucose 20% or infusion of human soluble insulin will be initiated in order to obtain a plasma glucose target of 5.5 mmol/L (100 mg/dL) \pm 10%. The insulin infusion should be stopped completely if glucose has to be infused and vice versa. When the plasma glucose target of 5.5 mmol/L (100 mg/dL) \pm 10% is reached, a continuous insulin infusion (2.5 mU/kg/min) of human soluble insulin will be applied for 120 min to acutely raise and maintain serum insulin concentrations. Blood glucose will be clamped at the concentration of 5.5 mmol/L by a variable infusion of glucose 20%. Blood samples for measurement of plasma glucose concentrations will be obtained at 5 min interval, for measurement of insulin concentrations and platelet activity every 30 min (timepoints 0, 60, 90, 120 min.) throughout the clamp. For safety reasons, serum potassium will be measured at start of the clamp procedure and after that at the discretion of the investigator. Potassium will be substituted at discretion of the investigator. After 120 min, the clamp experiment is completed. Subjects will receive a meal and will remain at the study center until stabilisation of PG. When patients are in a normoglycemic state and in a good clinical condition, determined by the investigator, they will be discharged equipped with carbohydrates for hypoglycemia prevention.

	Title: DIAPLATE-STUDY	Protocol No: Version 3.5	Sponsor: Medical University of Graz	Date: 13th February 2018
--	--------------------------	-----------------------------	--	-----------------------------

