At approximately 07:00, two intravenous cannulas (catheters) will be inserted: one cannula will be inserted in an antecubital vein of a forearm for sampling of serial measurements of plasma glucose (approximately every 5-30 min, depending on the clamp procedure and safety). The hand will be placed in a heated environment to enable drawing of arterialised-venous blood. For controlled variable infusion of glucose 20% and infusion of human soluble insulin (40 IU Actrapid®, 100 IU/ml in 99.6 mL saline), an antecubital vein of the contralateral arm will be cannulated. Both cannulas will be kept open by a slow continuous 0.9% saline infusion. After the baseline blood samples for blood glucose, insulin, counter regulatory hormone parameters and platelet activity have been taken, the hyperinsulinemic hypoglycemic clamp will be started. A variable i.v. infusion of glucose 20% or infusion of human soluble insulin will be initiated in order to obtain a plasma glucose target of 5.5 mmol/L (100 mg/dL) \pm 10%. When the plasma glucose target of 5.5 mmol/L (100mg/dL) \pm 10% is reached the high constant insulin infusion (2.5 mU/kg/min) will be initiated. After 30 minutes the plateau 5.5mmol/L will be started. After 30 min on the 5.5 mmol/L plateau the glucose infusion will be interrupted, the PG will be allowed to decline to 3.5 mmol/L and by restarting the variable glucose infusion, kept stable at 3.5 mmol/L. Thereafter the glucose infusion will be interrupted and the PG will be allowed to decline to 2.5 mmol/L or a nadir at a higher concentration in case 2.5 mmol/L cannot be reached or symptoms of hypoglycaemia are unacceptable. By restarting the variable glucose infusion the PG will be kept stable at 2.5 mmol/L or nadir and assessments on the plateau will be performed. After 15 min on the 2.5 mmol/L or nadir plateau the constant high insulin infusion will be terminated. Starting at time point 25 min on the 2.5 mmol/L or nadir plateau the glucose infusion will be tapered off, if possible, to allow a spontaneous recovery from hypoglycaemia. PG will not be allowed to fall below 2.2 mmol/L. If PG has not reached 4.0 mmol/L 45 min after termination of the constant high insulin infusion, a constant high glucose infusion (5.5 mg/kg/min) will be initiated to increase PG to a level of 4.0 mmol/L. When reaching the PG level of 4.0 mmol/L assessments will be performed and blood samples will be taken. The PG will then be increased to 5.5 mmol/L for safety reasons and the clamp terminated, if deemed safe by the investigator. PAP and CRH samples will be obtained at the end of each plateau phase as well as after recovery from hypoglycaemia at PG 100mg/dl (see figure 1).

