7. STATISTICAL ANALYSES

7.1 SAMPLE SIZE AND POWER CONSIDERATIONS

We have shown previously that light transmittance aggregometry (LTA) based on ADP activation in a population of subjects with type 2 diabetes is $70\pm12\%$ (Bethel MA et al. Diabetic Medicine 2016). For a clinically relevant difference in LTA from baseline to hypoglycaemia of 10% and assuming a standard deviation of 12%, 14 subjects are needed to achieve a power of 80% using a paired t-test with a 0.05 two-sided significance level. To account for potential study drop-outs, a maximum of 16 subjects will be included in this trial if required.

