7.2 DATA ANALYSIS

The analysis of the collected data in the study will be performed with SAS v9.4. Demographic and baseline characteristics will be summarized descriptively. Continuous variables will be presented as means, standard deviation, median, minimum and maximum, for categorical data frequencies and relative frequencies will be used.

The primary endpoint changes in platelet activation measured by light transmittance aggregometry based on ADP activation from baseline to the end of the hypoglycaemia phase (i.e. 45 mg/dl for 30 minutes) at visit 3 will

	Title: DIAPLATE-STUDY	Protocol No: Version 3.5	Sponsor: Medical University of Graz	Date: 13th February 2018
--	--------------------------	-----------------------------	--	-----------------------------

be analysed using a paired t-test. Data will be adjusted for platelet activation variability captured at the euglycemic clamp visit. (Details will be outlined in the statistical analysis plan). A two-sided p-value of <0.05 is considered to indicate statistical significance.

The secondary endpoints will be presented descriptively and changes over the time points (from baseline to the end of the hypoglycaemia phase at visit 3) will be explored using parametric or non-parametric tests for dependent data. If applicable, linear models, accounting for the repeated measurements will be considered to investigate changes from the end of the hypoglycaemic clamp (last measurement of visit 3) to one day (visit 4) and 6±1 days after the clamp (visit 5) and changes during different states of hypoglycaemia at visit 3.

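### The day-1 and one-week platelet samples are analysed without a pre-clamp reference or a clamp control, so the plan cannot show how long an effect of hypoglycaemia lasts

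*Combined protocol and SAP*

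**What the plan says.** Section 1 states the aim: "In addition we aim to investigate for how long these potential effects sustain after the hypoglycaemic event". Section 2.4 turns it into secondary outcomes, for example platelet marker changes "from the end of the hypoglycaemic clamp to one day after the clamp", with a matching set for one week. Section 7.2 says that linear models for repeated measurements will be considered, where applicable, "to investigate changes from the end of the hypoglycaemic clamp (last measurement of visit 3) to one day (visit 4") and to Visit 5.

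Platelet activity is sampled at Visits 2, 3, 4 and 5 only (Table 1, section 5.3.7). Visit 2, the euglycaemic clamp, ends at 120 minutes with a meal and discharge. Nothing is drawn one day or one week after it.

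Both clamp visits include a platelet sample before the clamp starts. For Visit 2: "After the baseline blood samples for blood glucose, insulin and platelet activity have been taken (timepoint 0 min"). For Visit 3: "After the baseline blood samples for blood glucose, insulin, counter regulatory hormone parameters and platelet activity have been taken". Section 7.2 mentions the euglycaemic visit only in the paragraph on the primary endpoint, as an adjustment whose details are left to a separate SAP that is not among the documents.

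**The concern.** Two things are missing from the follow-up analysis.

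- **A pre-clamp reference.** Whether activation persists is a question about the distance from the pre-clamp level. The planned contrast measures the distance from the end of the clamp. It may even start from the post-recovery sample, since section 5.2.3 places a sample there, after the hypoglycaemic plateau.
- **A clamp control.** Both clamps share the insulin infusion rate, cannulation, bed rest and repeated sampling. Any delayed effect of these, or drift between visits, is mixed with any effect of hypoglycaemia at Visits 4 and 5. The euglycaemic clamp separates them only in the acute phase.

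At stake is a statement that platelet activation lasts for a day or a week after hypoglycaemia. The analysis as written would not support it.

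**Working it through.** **Inputs.** Section 7.1 assumes a "clinically relevant difference in LTA from baseline to hypoglycaemia of 10% and assuming a standard deviation of 12"% and states that "14 subjects are needed to achieve a power of 80% using a paired t-test with a 0.05 two-sided significance level". The follow-up contrasts have no stated figure.

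**The plan's own figure.** Exact noncentral t, paired test, difference 10, SD of the difference 12: power is 78.8% at n = 13 and 82.2% at n = 14. The stated 14 reproduces, with 12 used as the SD of a paired difference.

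**What the planned contrast measures.** Let h be the rise above the pre-clamp level at the last Visit 3 sample and r the rise remaining at Visit 4 or 5. The planned change is r − h. With illustrative values:

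| h | r | r − h | Meaning |
|---|---|---|---|
| 10 | 10 | 0 | full persistence |
| 0 | 0 | 0 | no activation at any time |
| 10 | 5 | −5 | half persists |
| 5 | 0 | −5 | full recovery |

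The same planned result fits opposite conclusions. Moreover, r is itself the sum of a hypoglycaemia effect, a clamp effect and drift.

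**Precision of contrasts available from the planned samples.** Assume equal variance at each visit and equal correlation between visits. The within-visit SD is then 12/√2 = 8.49. A contrast with coefficients c has SD = 8.49 × √(Σc²), and its 95% half-width is 2.160 × SD/√14.

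| Contrast | Σc² | SD | Half-width | Power for 10 points |
|---|---|---|---|---|
| Visit 4 or 5 − Visit 3 pre | 2 | 12.0 | 6.9 | 82% |
| Visit 4 or 5 − mean of Visit 2 pre and Visit 3 pre | 1.5 | 10.4 | 6.0 | 91% |
| Visit 3 pre − Visit 2 pre | 2 | 12.0 | 6.9 | 82% |
| (Visit 5 − Visit 3 pre) − (Visit 3 pre − Visit 2 pre) | 6 | 20.8 | 12.0 | 38.5% |

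If 12 is instead a between-subject SD, with an assumed between-visit correlation of 0.3 to 0.8, the half-widths range from 8.2 to 4.4 (first and third rows), 7.1 to 3.8 (second) and 14.2 to 7.6 (fourth).

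**What the two pre-clamp samples can show.** Suppose hypoglycaemia has no lasting effect, but each clamp leaves a shift c.

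- *Shift present at Visit 5 but gone by the next pre-clamp sample:* Visit 3 pre − Visit 2 pre averages 0, while Visit 5 − Visit 3 pre averages c. The check is silent and the bias is full.
- *Lasting shift that does not accumulate:* the check averages c, while Visit 5 − Visit 3 pre averages 0. Against the mean of both pre-clamp samples the bias is c/2.
- *Accumulating shift:* both average c. Only here does the check reveal a bias in Visit 5 − Visit 3 pre.

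**Would requiring the one-week change to exceed the pre-clamp change help?** I simulated 200,000 trials with n = 14, independent within-person errors, and a clamp shift at Visit 5 only. Among significant rises, the rule passed 99.7%, 99.6% and 99.5% at shifts of 0.5, 0.75 and 1.0 within-visit SD. It filters out almost nothing.

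**Timing.** Table 1 puts Visit 3 at 10–24 days after Visit 2. The section heading counts 10–24 days from Visit 1; with Visit 2 at 2–10 days after Visit 1, this gives 10 − 10 = 0 to 24 − 2 = 22 days after Visit 2. Visit 5 is 6±1 days after Visit 4 in Table 1, hence 6–8 days after the clamp. In the text of section 5.2.4 and in section 7.2 it is 6±1 days after the clamp, hence 5–7.

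**The case against.** The case on the other side is substantial.

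- *The outcomes are exploratory.* They are secondary and mostly descriptive, in a single-arm mechanistic trial. This stands, and it limits the weight of the point.
- *The wording is already cautious.* Objectives and outcomes mostly speak of time after the clamp. This stands too; the causal phrasing is in the introduction's aim.
- *A reader could add the acute change to the follow-up change and recover the change from pre-clamp.* That works for a point estimate if the data are complete and both changes use the same Visit 3 sample. Section 7.2 does not secure the latter, and it plans no interval for the sum.
- *The separate SAP may add an analysis.* It may, so one cannot say that the trial will ignore the pre-clamp samples. It cannot create day-1 or one-week samples after the euglycaemic clamp.

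A reader might also infer that the two pre-clamp samples form a free control that licenses attribution to hypoglycaemia. They do not: the comparison is blind to exactly the transient clamp effect that would bias day 1 and one week, and a formal difference of changes is imprecise (half-width 12 points).

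Nor do false-attribution rates such as 23%, 45% and 69%, for clamp-only shifts of 0.5, 0.75 and 1.0 within-visit SD, describe this plan. They are arithmetically right, but the shifts are assumed and the test is Visit 5 against Visit 3 pre-clamp, which section 7.2 does not plan.

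**Conclusion.** The point holds for the follow-up outcomes. As written, section 7.2 cannot show whether activation at day 1 or one week is above its pre-clamp level, and the design cannot attribute such a change to hypoglycaemia alone. The first gap can be closed with samples already planned, to about ±6.9 points against Visit 3 pre-clamp, or ±6.0 against the mean of both pre-clamp samples if there is no drift between them. The second cannot be closed by analysis, so the wording must carry it.

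The figures rest on n = 14, 12 as the SD of a paired difference, and equal variance and correlation across visits. The documents do not support a claim that the trial will report a clamp effect as a hypoglycaemia effect; that would be an inference about future reporting. The primary outcome is unaffected.

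**What to change.** In section 7.2 or the SAP:

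1. Fit one repeated-measures model per platelet parameter to Visit 2 pre-clamp, Visit 3 pre-clamp, Visit 4 and Visit 5. Report the Visit 4 and Visit 5 changes from the pre-clamp level with 95% CIs. State which pre-clamp reference is the main one; the mean of the two gains precision by assuming no shift between them.
2. Report Visit 3 pre-clamp minus Visit 2 pre-clamp with its 95% CI, only as a check of between-visit drift and of a long-lasting or accumulating clamp effect. Do not make attribution depend on a follow-up change exceeding it.
3. Describe the day-1 and one-week changes as following the hypoglycaemic clamp, and say that no matched samples follow the euglycaemic clamp.
4. State which sample is the last Visit 3 measurement.
5. Reconcile the Visit 3 and Visit 5 timings, since they determine what the drift check and the one-week change mean.
6. Note that the pre-clamp samples appear to come from the heated-hand cannula (arterialised-venous), whereas Visit 4 is plain venous sampling. The drift check cannot capture that difference.

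Cost: analysis text and a few more estimates, with no added samples or visits. Downsides: the drift check is partial; it is not clearly available for IL-6, vWF, PAI-1, VCAM and ICAM, which the Visit 2 baseline list does not name; and the duration claim becomes weaker.
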